#### 5.3 Analysis of population characteristics

#### 5.3.1 Descriptive statistics

All background data such as patient characteristics, socio-economic characteristics, endometriosis pattern and gynecological history, family and medical history, concomitant medication as well as mood will be described by presenting frequency distributions and/or basic summary statistics (number of patients with an observation [n], mean, standard deviation [SD], median, 25th [Q1] and 75th [Q3] percentiles, minimum [Min] and maximum [Max]). Unless otherwise specified, the mean and median for a continuous variable will be listed to 1 more decimal place than the original (raw) values and the SD will be listed to 2 more decimal places than the original values. The minimum and maximum will be listed to the same number of decimal places as the original values.

Categorical variables will be summarized using frequencies and percentages. Each table will list both absolute and relative numbers (%), providing the total amount of available data for each variable. Total number of women (100%) for the presented (sub-) population is given in the first line of each table. Additional categories may be derived from data and are denoted by <<CATEGORY>> in the table templates. Percentages will be listed to 2 decimal places. In cases where the percentage calculated is > 0% and < 0.01%, three decimal places will be listed with the absolute value.

In addition, age-standardized proportions are presented for selected baseline characteristics, history of co-morbidity, risk markers and co-medication. Therefore, the most represented cohort will used as the referenced standard population.

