#### 5.3.2 Stratifying factors

The numbers of patients enrolled and included in the analysis populations will be tabulated by defined stratifying variables for the AT and ITT population, if appropriate.

Baseline and follow-up population characteristics will be presented for the AT and ITT population and stratified by

Supporting document SOP BMT 01.09 – Doc 5002.02 – Effective date 21.03.2017

- (1) Country
- (2) EMT user type: starter vs. switcher vs. restarter
- (3) Diagnostic classification: Diagnosis confirmed by surgery vs. diagnosis based on clinical symptoms,

if not otherwise specified.

The analysis of the primary and secondary outcomes will be presented for the AT population, anemia and depression additionally for the ITT population. Primary and secondary outcomes are stratified by subgroups if appropriate:

- (1) Country
- (2) EMT user type: starter vs. switcher vs. restarter
- (3) Diagnostic classification: Diagnosis confirmed by surgery vs. diagnosis based on clinical symptoms

Selected outcomes regarding the baseline risk (lifetime history of co-morbidity, risk markers, co-medication, socio-demographic and lifestyle data), will be additionally displayed by subgroups as follows:

- (1) Age categories: < 20 vs. 20 to < 30 vs. 30 to < 40 vs. >= 40
- (2) Age standardized

Additional subgroups will be added for selected outcomes if appropriate.

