#### 5.4.1 Incidence measures

The *incidence rate* (IR) measures the occurrence of new cases per unit of person-time.

$$IR = \frac{Number\ of\ new\ cases}{Total\ follow - up\ time}$$

The incidence rate takes into consideration the patient-specific follow-up time and it assumes a constant hazard rate. For each of n subjects the time  $t_k (k=1,...,K)$  to: (1) the end of the risk period, if recurrent events are allowed or (2) to the first occurrence of a certain event is observed. If the event was not experienced, the (censored) time to the end of the risk period is observed.

In the present study, women-years are conducted as a unit of person-time. Incidence rates are shown per 10^4 women-years (WY) unless otherwise specified.

The *incidence rate ratio* (IRR) is the proportion of two incidence rate estimates.

$$IRR = \frac{Incidence\ rate\ of\ treatment\ group}{Incidence\ rate\ of\ control\ group}$$

Supporting document SOP BMT 01.09 – Doc 5002.02 – Effective date 21.03.2017

The incidence rate ratio gives a measure of how much more likely an event occurs in subjects under exposure (treatment group) than in subjects who were not exposed (control group).

The *incidence proportion* (IP) measures the occurrence of new cases in relation to the size of the population at risk within a given period of time (cumulative incidence).

$$IP = \frac{Number\ of\ new\ cases}{Size\ of\ population\ at\ risk}$$

Exact 95% confidence intervals for prevalence, incidence proportion, incidence rate, and incidence rate ratio will be calculated in accordance with Clopper and Pearson[9].

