#### 6.2.2 Definition of subgroups

Variable label	Definition
Country	Germany vs. Poland vs. Hungary vs. Switzerland vs. Russia vs. Ukraine
Long-term user	15 months or more of continuous EMT intake
EMT user type	Starter vs. restarter vs. switcher
Diagnosis classification	Diagnosis of endometriosis confirmed via surgery / laparoscopy vs. diagnosis based on clinical symptoms
Age categories	< 20 vs. 20 to < 30 vs. 30 to < 40 vs. >= 40
Age-standardization	Referenced population: NAED cohort

12 ICD10-Codes Version 2009

13 ATC-Codes Version 2010

14 OPS-Codes Version 2009

Supporting document SOP BMT 01.09 – Doc 5002.02 – Effective date 21.03.2017

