#### Section C-3 Other Safety Outcomes

The analysis of other safety outcomes (Section C3) is stratified by country, EMT user type and diagnosis classification.

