#### Section C-3 Other safety outcomes

#### Section C-3.1 Incidence rate of confirmed thromboembolic events

Table C-3.1.1 Incidence rate of confirmed thromboembolic events, AT population, Complete cohort

	DNG		OAED			NAED		Ex-use	Allocation unknown	Total
		GnRH-a	Danazol	All OAED	СНС	Other progestin	All NAED			
Number of women years	xx	XX	XX	xx	xx	xx	xx	xx	XX	xx
ALL VTE & ATE	xx	xx	xx	XX	xx	XX	xx	xx	xx	xx
IR* (95% CI)	xx.x (xx.x-x.x)	xx.x (xx.x-x.x)	xx.x (xx.x-x.x)	xx.x (xx.x-x.x)	xx.x (xx.x-x.x)					
Thereof										
All VTE	xx	xx	xx	xx	xx	xx	xx	xx	xx	xx
	xx.x (xx.x-x.x)	xx.x (xx.x-x.x)	xx.x (xx.x-x.x)	xx.x (xx.x-x.x)	xx.x (xx.x-x.x)					
Thereof										
PE	xx	xx	xx	xx	xx	xx	xx	xx	xx	xx
	xx.x (xx.x-x.x)	xx.x (xx.x-x.x)	xx.x (xx.x-x.x)	xx.x (xx.x-x.x)	xx.x (xx.x–x.x)	xx.x (xx.x-x.x)	xx.x (xx.x-x.x)	xx.x (xx.x-x.x)	xx.x (xx.x-x.x)	xx.x (xx.x-x.x)
ALL ATE (TIAs included)	xx	xx	xx	XX	xx	XX	XX	XX	xx	xx
	xx.x (xx.x-x.x)	xx.x (xx.x-x.x)	xx.x (xx.x-x.x)	xx.x (xx.x-x.x)	xx.x (xx.x-x.x)					
Thereof										
AMI										
Ischemic stroke										
TIA										
ALL ATE (TIAs excluded)										

Note: \* Incidence rate is shown per 10^4 women years.

Table C-3.1.2	Incidence rate of confirmed thromboembolic events, AT population, Starter
Table C-3.1.3	Incidence rate of confirmed thromboembolic events, AT population, Switcher
Table C-3.1.4	Incidence rate of confirmed thromboembolic events, AT population, Restarter
Table C-3.1.5	Incidence rate of confirmed thromboembolic events, AT population, Diagnosis confirmed by surgery
Table C-3.1.6	Incidence rate of confirmed thromboembolic events, AT population, Diagnosis based on clinical symptoms
Table C-3.1.7	Incidence rate of confirmed thromboembolic events, AT population, Germany
Table C-3.1.8	Incidence rate of confirmed thromboembolic events, AT population, Poland
Table C-3.1.9	Incidence rate of confirmed thromboembolic events, AT population, Hungary
Table C-3.1.10	Incidence rate of confirmed thromboembolic events, AT population, Switzerland
Table C-3.1.11	Incidence rate of confirmed thromboembolic events, AT population, Russia
Table C-3.1.12	Incidence rate of confirmed thromboembolic events, AT population, Ukraine

Supporting document SOP BMT 01.09 – Doc 5002.02 – Effective date 21.03.2017

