#### Section C-3.2 Incidence rate of fatal cases (all deaths)

Table C-3.2.1 Incidence rate of fatal cases (all deaths), AT population, Complete cohort

	DNG		OAED		NAED		Ex-use	Allocation unknown	Total	
		GnRH-a	Danazol	All OAED	CHC	Other progestin	All NAED			
Number of women years	xx									
All deaths  IR* (95% CI)	xx xx.x (xx.x–x.x)									
Reason << Category >>	xx xx.x (xx.x–x.x)	xx xx.x (xx.x–x.x)		xx xx.x (xx.x–x.x)	xx xx.x (xx.x–x.x)	xx xx.x (xx.x–x.x)	xx xx.x (xx.x-x.x)	xx xx.x (xx.x–x.x)	xx xx.x (xx.x–x.x)	xx xx.x (xx.x–x.x)

Note: \* Incidence rate is shown per 10^4 women years.

Table C-3.2.2	Incidence rate of fatal cases (all deaths), AT population, Starter
Table C-3.2.3	Incidence rate of fatal cases (all deaths), AT population, Switcher
Table C-3.2.4	Incidence rate of fatal cases (all deaths), AT population, Restarter
Table C-3.2.5	Incidence rate of fatal cases (all deaths), AT population, Diagnosis confirmed by surgery
Table C-3.2.6	Incidence rate of fatal cases (all deaths), AT population, Diagnosis based on clinical symptoms
Table C-3.2.7	Incidence rate of fatal cases (all deaths), AT population, Germany
Table C-3.2.8	Incidence rate of fatal cases (all deaths), AT population, Poland
Table C-3.2.9	Incidence rate of fatal cases (all deaths), AT population, Hungary
Table C-3.2.10	Incidence rate of fatal cases (all deaths), AT population, Switzerland
Table C-3.2.11	Incidence rate of fatal cases (all deaths), AT population, Russia
Table C-3.2.12	Incidence rate of fatal cases (all deaths), AT population, Ukraine

Supporting document SOP BMT 01.09 – Doc 5002.02 – Effective date 21.03.2017

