#### Section C-3.5 Incidence rate of malignant neoplasms by organ system

Table C-3.5.1 Incidence rate of malignant neoplasms by organ system, AT population, Complete cohort

	DNG		OAED			NAED		Ex-use	Allocation unknown	Total
		GnRH-a	Danazol	All OAED	СНС	Other progestin	All NAED			
Number of women years	xx	xx	xx	xx	xx	xx	xx	xx	xx	xx
Malignant neoplasms	xx	xx	xx	xx	xx	xx	xx	xx	xx	xx
IR* (95% CI)	xx.x (xx.x–x.x)	xx.x (xx.x-x.x)	xx.x (xx.x-x.x)	xx.x (xx.x-x.x)	xx.x (xx.x–x.x)	xx.x (xx.x-x.x)	xx.x (xx.x-x.x)	xx.x (xx.x-x.x)	xx.x (xx.x-x.x)	xx.x (xx.x–x.x)
Breast	xx	xx	xx	xx	xx	xx	xx	xx	xx	xx
	xx.x (xx.x-x.x)	xx.x (xx.x-x.x)	xx.x (xx.x-x.x)	xx.x (xx.x-x.x)	xx.x (xx.x-x.x)					
Cervix uteri	XX	xx	xx	XX	XX	xx	XX	xx	xx	XX
	xx.x (xx.x-x.x)	xx.x (xx.x-x.x)	xx.x (xx.x-x.x)	xx.x (xx.x-x.x)	xx.x (xx.x-x.x)					
Corpus uteri and uterus	xx	xx	xx	xx	XX	xx	XX	xx	xx	xx
unspecified	xx.x (xx.x-x.x)	xx.x (xx.x-x.x)	xx.x (xx.x-x.x)	xx.x (xx.x-x.x)	xx.x (xx.x-x.x)					
Ovary	xx	xx	xx	xx	XX	xx	xx	XX	xx	xx
	xx.x (xx.x-x.x)	xx.x (xx.x-x.x)	xx.x (xx.x-x.x)	xx.x (xx.x-x.x)	xx.x (xx.x-x.x)					
Fallopian tube	XX	XX	XX	XX	XX	XX	XX	xx	XX	XX
	xx.x (xx.x–x.x)	xx.x (xx.x–x.x)	xx.x (xx.x-x.x)	xx.x (xx.x–x.x)	xx.x (xx.x–x.x)	xx.x (xx.x-x.x)	xx.x (xx.x–x.x)	xx.x (xx.x–x.x)	xx.x (xx.x-x.x)	xx.x (xx.x–x.x)
Vagina	XX	XX	xx	XX	XX	xx	XX	xx	xx	XX
	xx.x (xx.x–x.x)	xx.x (xx.x–x.x)	xx.x (xx.x-x.x)	xx.x (xx.x–x.x)	xx.x (xx.x–x.x)	xx.x (xx.x-x.x)	xx.x (xx.x–x.x)	xx.x (xx.x–x.x)	xx.x (xx.x-x.x)	xx.x (xx.x–x.x)
Vulva	XX	XX	XX	XX	XX		XX	XX	XX	XX
	xx.x (xx.x–x.x)	xx.x (xx.x–x.x)	xx.x (xx.x-x.x)	xx.x (xx.x-x.x)	xx.x (xx.x–x.x)					
Unspecified genital	XX	XX	XX	XX	XX	XX	XX	XX	XX	XX
	xx.x (xx.x-x.x)	xx.x (xx.x-x.x)	xx.x (xx.x–x.x)	xx.x (xx.x–x.x)	xx.x (xx.x–x.x)	xx.x (xx.x–x.x)	xx.x (xx.x–x.x)	xx.x (xx.x-x.x)	xx.x (xx.x–x.x)	xx.x (xx.x–x.x)
Placenta	XX		XX	XX	XX	XX	XX	XX	XX	XX
	xx.x (xx.x-x.x)	xx.x (xx.x-x.x)	xx.x (xx.x–x.x)	xx.x (xx.x–x.x)	xx.x (xx.x–x.x)	xx.x (xx.x–x.x)	xx.x (xx.x–x.x)	xx.x (xx.x-x.x)	xx.x (xx.x–x.x)	xx.x (xx.x–x.x)
Subtotal of gyn. cancer	хх	XX	XX	XX	XX	XX	хх	XX	XX	XX

Supporting document SOP BMT 01.09 – Doc 5002.02 – Effective date 21.03.2017

	xx.x (xx.x–x.x)	xx.x (xx.x–x.x)	xx.x (xx.x-x.x)	xx.x (xx.x-x.x)	хх.х (хх.х–х.х)	xx.x (xx.x–x.x)	xx.x (xx.x-x.x)	хх.х (хх.х– х.х)	xx.x (xx.x– x.x)	xx.x (xx.x-x.x)
Lip, oral cavity and	xx	XX	xx							
pharynx	xx.x (xx.x-x.x)	xx.x (xx.x-x.x)	xx.x (xx.x-x.x)							
Digestive organs	xx	xx	xx							

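### Thromboembolism, death and cancer rates are set side by side for DNG, OAED and NAED as crude rates only, so an age difference between cohorts can be mistaken for a drug effect

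*SAP*

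**What the plan says.** SAP 5.4.1 defines the incidence rate as one that "measures the occurrence of new cases per unit of person-time", that is, new cases divided by total follow-up time. This crude rate is the only summary in three mock tables:

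- C-3.1.1: "Incidence rate of confirmed thromboembolic events, AT population, Complete cohort"
- C-3.2.1: "Incidence rate of fatal cases (all deaths), AT population, Complete cohort"
- C-3.5.1: "Incidence rate of malignant neoplasms by organ system, AT population, Complete cohort"

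Each table gives women-years, events and a rate per 10,000 women-years with a 95% interval, in adjacent columns for DNG, OAED and NAED. Malignant neoplasms also appear as a crude row in C-3.3.1 (serious adverse events) and C-3.4.1 (long-term users). Both of those tables have a cardiovascular row as well.

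On breakdowns, SAP section 8 says: "The analysis of other safety outcomes (Section C3) is stratified by country, EMT user type and diagnosis classification". Age is not listed.

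On age, SAP 5.3.1 says that "age-standardized proportions are presented for selected baseline characteristics, history of co-morbidity, risk markers and co-medication". SAP 5.3.2 gives the age categories (<20, 20 to <30, 30 to <40, 40 and over) and age-standardization the same scope: "Selected outcomes regarding the baseline risk (lifetime history of co-morbidity, risk markers, co-medication, socio-demographic and lifestyle data), will be additionally displayed by subgroups". SAP 6.2.2 names the standard: "Referenced population: NAED cohort". SAP 5.3.1 instead takes the largest cohort as the standard.

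**The concern.** The primary objective is the safety of DNG and of the other hormonal treatments, including the absolute risk of rare serious outcomes. SAP 5.4 says that SAEs associated with use of DNG, OAED and NAED will be assessed. Readers of three adjacent columns will compare them.

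The study does not interfere with prescribing, so physicians' choices form the cohorts. The SAP itself allows that ages may differ between cohorts: it lists age as a prognostic factor for all three primary outcomes (5.4.2) and age-standardizes baseline co-morbidity (5.3.1). For cancer, death and VTE/ATE it makes no such provision. An age imbalance could then create an apparent excess under DNG or hide a real one.

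**Working it through.** No figure in the plan is in dispute, so the check has three parts.

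**1. Where the SAP uses age**

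| Item | Age used? | Source |
|---|---|---|
| Baseline characteristics | Yes: by category and standardized | 5.3.1, 5.3.2; Tables B-9.2.3 to B-9.2.12 |
| Anemia, depression, treatment failure | Yes: covariate in the Cox models | 5.4.2, Appendix III, Section D |
| VTE/ATE, deaths, malignancies | No: crude; repeated by user type, diagnosis class and country | Section 8; C-3.1, C-3.2, C-3.5 |
| SAEs by organ system, all and long-term users | No: crude | C-3.3, C-3.4 |

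The only age-standardized tables are B-9.2.11 and B-9.2.12, both for baseline data. Section D limits rate ratios and regression to the primary outcomes. The adolescent tables (C-2.2 to C-2.4) cover anemia, depression and discontinuation only. SAP 5.3.2 ends by allowing further subgroups where appropriate, but it names no outcome and no age adjustment.

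**2. Possible size of the distortion (assumed inputs)**

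The documents give neither age by cohort nor age-specific rates. Assume no drug effect and a rate that multiplies by f from one SAP age category to the next, so the relative rates are 1, f, f², f³. With w as the share of women-years in each category:

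crude ratio = Σ(w_DNG × rate) / Σ(w_NAED × rate)

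Assumed shares over the four categories:
- DNG: 2/25/48/25% (mean age about 35)
- NAED, mix 1: 6/38/40/16% (mean age about 32)
- NAED, mix 2: 10/45/33/12% (mean age about 30)

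Example with f = 2 and mix 1:
- DNG: 0.02×1 + 0.25×2 + 0.48×4 + 0.25×8 = 4.44
- NAED: 0.06×1 + 0.38×2 + 0.40×4 + 0.16×8 = 3.70
- Ratio: 4.44/3.70 = 1.20

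| f | DNG sum | NAED mix 1: sum, ratio | NAED mix 2: sum, ratio |
|---|---|---|---|
| 1.5 | 2.319 | 2.070, **1.12** | 1.923, **1.21** |
| 2 | 4.44 | 3.70, **1.20** | 3.28, **1.35** |
| 3 | 11.84 | 9.12, **1.30** | 7.66, **1.55** |

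With equal mixes the ratio is 1.00. With the mixes swapped it is the reciprocal, from 1/1.12 = 0.89 to 1/1.55 = 0.65. A simpler model, ratio = g^(s/10) for a mean-age shift of s years and a rate multiplying by g per decade, gives 1.08, 1.15 and 1.25 for s = 2, and 1.22, 1.41 and 1.73 for s = 5 (g = 1.5, 2, 3). Under either model, standardizing to a common age distribution returns 1.00.

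**3. How many events there would be**

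The planned women-years are 8,400 for DNG and 4,200 for the reference cohort (SAP section 4, Table 2). Take 10 events per 10,000 women-years, the top of the rare-event range quoted there:

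- DNG: 8,400 × 10/10,000 = 8.4 events; OAED: 4,200 × 10/10,000 = 4.2. With 8 vs 4 events the exact 95% interval for the rate ratio is about 0.27 to 4.5.
- If NAED held all remaining women-years (an assumption), 84,000 − 8,400 − 4,200 = 71,400 gives about 71 events. With 8 vs 71 the interval is about 0.40 to 2.0.

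At 1 per 10,000, the expected counts for DNG and OAED are 0.84 and 0.42.

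**The case against.** The strongest reply is that these tables are descriptive. Crude rates are the right measure of absolute risk, which is a stated aim, and no test or ratio between cohorts is planned for these outcomes. That stands, and it is why the crude rates should stay. It does not make adjacent columns comparable.

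A second reply is that noise outweighs the bias. For DNG vs OAED this is largely right: an interval of about 0.27 to 4.5 dwarfs a distortion of 1.1 to 1.55, and splitting about four events over four age bands leaves empty strata. For DNG vs NAED the point carries more weight. Sparse data widen an interval; they do not remove confounding.

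Third, age by cohort is tabulated in B-1.1, and serious events also get individual causality assessment (protocol Appendix 3). A reader could therefore see an imbalance and would have some other evidence on attribution. But no age-specific events or women-years are shown for these outcomes, so the reader could not correct for it.

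Two stronger readings are tempting and are not supported. One is that age differences will be read as drug effects: the documents give no age mix, so neither the existence nor the direction of an imbalance is known. The other is that the three tables are the only result for these outcomes: malignancies also appear in C-3.3.1 and C-3.4.1. Those rows are crude too, so they add the same problem rather than an answer to it.

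**Conclusion.** The omission is confirmed by the text: VTE/ATE, deaths and malignancies are compared across cohorts only through crude rates, while the SAP's own age bands and standard population are confined to baseline data. The consequence is conditional. If cohort ages differ, the columns can mislead, by a factor of about 1.1 to 1.55 under the assumed mixes, or the reciprocal if DNG users are younger; with equal ages there is no distortion. The gain from adjustment is mainly in DNG vs NAED; for DNG vs OAED the expected event counts are too small to promise much. This should be fixed as an inexpensive improvement. It does not affect the three primary hypotheses.

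**What to change.** - Keep the crude rates in C-3.1.1, C-3.2.1 and C-3.5.1 as absolute risks.
- For the totals only (VTE and ATE combined, all VTE, all deaths, all malignant neoplasms), add a rate directly standardized to the NAED women-years over the four SAP age bands. Leave the organ-level rows crude.
- State the age basis. SAP 6.2 calculates age at study entry, while follow-up runs to 7 years, so the plan must say whether women-years are banded by entry age or attained age.
- Name NAED as the one standard population, as in 6.2.2, and bring 5.3.1 into line.
- Add an age-adjusted DNG vs NAED rate ratio (Mantel-Haenszel or Poisson), labelled descriptive. Add DNG vs OAED only where both groups reach the SAP 5.4.2 threshold of 5 confirmed events.
- Where a ratio is not shown, footnote that the crude columns are not age-comparable. Put the same footnote on the malignancy and cardiovascular rows of C-3.3.1 and C-3.4.1.

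Date of birth is already collected and the bands exist, so no new data are needed. The cost is some programming, wide intervals and possibly empty age strata, above all in OAED. The open-ended 40-and-over band will also leave some residual age confounding.

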### Section C-3.6 Incidence proportion of malformations

Table C-3.6.1 Incidence proportion of malformations, AT population, Complete cohort

	DNG		OAED			NAED		Allocation unknown	Total
		GnRH-a	Danazol	All OAED	СНС	Other progestin	All NAED		
Number of deliveries	xx	xx	xx	xx	xx	xx	xx	xx	xx
Malformations	xx	xx	xx	xx	xx	xx	xx	xx	xx
IP** (95% CI)	xx.x (xx.x-x.x)	xx.x (xx.x-x.x)	xx.x (xx.x-x.x)	xx.x (xx.x–x.x)	xx.x (xx.x–x.x)	xx.x (xx.x-x.x)	xx.x (xx.x-x.x)	xx.x (xx.x-x.x)	xx.x (xx.x-x.x)
Thereof last endometriosis treatment exposure									
At conception	xx	xx	xx	xx	XX	xx	XX	xx	xx
	xx.x (xx.x-x.x)	xx.x (xx.x-x.x)	xx.x (xx.x-x.x)	xx.x (xx.x-x.x)					
One cycle before	xx	xx	xx	XX	XX	XX	XX	xx	xx
conception	xx.x (xx.x-x.x)	xx.x (xx.x-x.x)	xx.x (xx.x-x.x)	xx.x (xx.x-x.x)					
More than one cycle	xx	xx	xx	XX	XX	xx	XX	xx	xx
before conception	xx.x (xx.x–x.x)	xx.x (xx.x-x.x)	xx.x (xx.x-x.x)	xx.x (xx.x–x.x)	xx.x (xx.x–x.x)	xx.x (xx.x-x.x)	xx.x (xx.x-x.x)	xx.x (xx.x–x.x)	xx.x (xx.x–x.x)

Note: \* Cohort allocation is based on the intake of the last endometriosis treatment before delivery.

Note: \*\*Incidence proportion is shown per 10^2 deliveries.

Table C-3.6.2	Incidence proportion of malformations, AT population, Starter
Table C-3.6.3	Incidence proportion of malformations, AT population, Switcher
Table C-3.6.4	Incidence proportion of malformations, AT population, Restarter
Table C-3.6.5	Incidence proportion of malformations, AT population, Diagnosis confirmed by surgery
Table C-3.6.6	Incidence proportion of malformations, AT population, Diagnosis based on clinical symptoms
Table C-3.6.7	Incidence proportion of malformations, AT population, Germany
Table C-3.6.8	Incidence proportion of malformations, AT population, Poland
Table C-3.6.9	Incidence proportion of malformations, AT population, Hungary
Table C-3.6.10	Incidence proportion of malformations, AT population, Switzerland
Table C-3.6.11	Incidence proportion of malformations, AT population, Russia
Table C-3.6.12	Incidence proportion of malformations, AT population, Ukraine

Supporting document SOP BMT 01.09 - Doc 5002.02 - Effective date 21.03.2017

Section C-3.7 Other outcomes of interest

Section C-3.8 Incidence rate of surgery / laparoscopy because of endometriosis

Section C-3.1 Incidence rate of surgery / laparoscopy because of endometriosis, ITT population, Complete cohort

	DNG		OAED			NAED		Ex-use	Allocation unknown	Total
		GnRH-a	Danazol	All OAED	СНС	Other progestin	All NAED			
Number of women years	XX	xx	XX	xx	xx	xx	xx	xx	xx	xx
Diagnostic surgical										
intervention	xx	xx	xx	xx	XX	xx	xx	xx	xx	xx
IR* (95% CI)	xx.x (xx.x-x.x)	xx.x (xx.x-x.x)	xx.x (xx.x-x.x)	xx.x (xx.x-x.x)	xx.x (xx.x-x.x)					
Therapeutic surgery	xx	xx	xx	XX	xx	XX	XX	XX	xx	XX
(laparoscopic)	xx.x (xx.x-x.x)	xx.x (xx.x-x.x)	xx.x (xx.x-x.x)	xx.x (xx.x-x.x)	xx.x (xx.x-x.x)					
Thereof										
Excisions of lesions /	xx	xx	xx	xx	xx	xx	xx	xx	xx	xx
adhesions	xx.x (xx.x-x.x)	xx.x (xx.x-x.x)	xx.x (xx.x-x.x)	xx.x (xx.x-x.x)	xx.x (xx.x-x.x)					
Removal of ovarian	xx	xx	xx	XX	XX	xx	XX	xx	xx	xx
cysts	xx.x (xx.x-x.x)	xx.x (xx.x-x.x)	xx.x (xx.x-x.x)	xx.x (xx.x-x.x)	xx.x (xx.x-x.x)					
Removal of ovary /	xx	xx	xx	XX	XX	xx	XX	xx	xx	XX
fallopian tubes	xx.x (xx.x-x.x)	xx.x (xx.x-x.x)	xx.x (xx.x-x.x)	xx.x (xx.x-x.x)	xx.x (xx.x-x.x)					
Hysterectomy	xx	xx	xx	XX	XX	xx	XX	xx	xx	xx
Hysterectority	xx.x (xx.x-x.x)	xx.x (xx.x-x.x)	xx.x (xx.x-x.x)	xx.x (xx.x-x.x)	xx.x (xx.x-x.x)					
Other	xx	XX	xx	xx	XX	xx	xx	xx	xx	xx
Other	xx.x (xx.x–x.x)	xx.x (xx.x-x.x)	xx.x (xx.x-x.x)	xx.x (xx.x-x.x)	xx.x (xx.x–x.x)	xx.x (xx.x-x.x)	xx.x (xx.x-x.x)	xx.x (xx.x-x.x)	xx.x (xx.x-x.x)	xx.x (xx.x-x.x)
Therapeutic surgery	xx	xx	xx	xx	xx	xx	xx	xx	xx	xx
(open abdominal) Thereof	xx.x (xx.x-x.x)	xx.x (xx.x-x.x)	xx.x (xx.x-x.x)	xx.x (xx.x–x.x)	xx.x (xx.x–x.x)	xx.x (xx.x–x.x)	xx.x (xx.x–x.x)	xx.x (xx.x-x.x)	xx.x (xx.x-x.x)	xx.x (xx.x–x.x)

Supporting document SOP BMT 01.09 – Doc 5002.02 – Effective date 21.03.2017

Excisions of lesions /	xx									
adhesions	xx.x (xx.x-x.x)									
Removal of ovarian	xx									
cysts	xx.x (xx.x-x.x)									
Removal of ovary /	xx									
fallopian tubes	xx.x (xx.x-x.x)									
I liveta va eta va.	xx									
Hysterectomy	xx.x (xx.x-x.x)									
Othor	xx									
Other	xx.x (xx.x-x.x)									
Therapeutic surgery										
(other, incl type	xx									
unknown)	xx.x (xx.x-x.x)									
Thereof										
Excisions of lesions /	xx									
adhesions	xx.x (xx.x-x.x)									
Removal of ovarian	xx									
cysts	xx.x (xx.x-x.x)									
Removal of ovary /	xx									
fallopian tubes	xx.x (xx.x-x.x)									
I liveta va eta va.	xx									
Hysterectomy	xx.x (xx.x-x.x)									
Out	xx									
Other	xx.x (xx.x-x.x)									

Note: \* Incidence rate is shown per 10^4 women years.

Table C-3.8.2	Incidence rate of surgery / laparoscopy because of endometriosis, AT population, Starter
Table C-3.8.3	Incidence rate of surgery / laparoscopy because of endometriosis, AT population, Switcher
Table C-3.8.4	Incidence rate of surgery / laparoscopy because of endometriosis, AT population, Restarter
Table C-3.8.5	Incidence rate of surgery / laparoscopy because of endometriosis, AT population, Diagnosis confirmed by surgery
Table C-3.8.6	Incidence rate of surgery / laparoscopy because of endometriosis, AT population, Diagnosis based on clinical symptoms
Table C-3.8.7	Incidence rate of surgery / laparoscopy because of endometriosis, AT population, Germany
Table C-3.8.8	Incidence rate of surgery / laparoscopy because of endometriosis, AT population, Poland
Table C-3.8.9	Incidence rate of surgery / laparoscopy because of endometriosis, AT population, Hungary
Table C-3.8.10	Incidence rate of surgery / laparoscopy because of endometriosis, AT population, Switzerland
Table C-3.8.11	Incidence rate of surgery / laparoscopy because of endometriosis, AT population, Russia
Table C-3.8.12	Incidence rate of surgery / laparoscopy because of endometriosis, AT population, Ukraine

Supporting document SOP BMT 01.09 – Doc 5002.02 – Effective date 21.03.2017

